1.2.4 Computer Aided Detection for screening (CAD)

An image-based national screening programme requires a large scanning capacity and produces many scans requiring interpretation by radiologists with the relevant experience and subspecialty training. It is important that a screening prostate MRI provides consistent results when performed across diverse centres and interpreted by different clinicians. There is interobserver variability in all radiological reporting but the rates for prostate MRI have not reached the level achieved with mammograms for breast cancer screening(34).

Computer-aided detection (CAD) or Artificial Intelligence (AI) systems can potentially be an utilised to reduce interobserver variability and improve radiological reporting capacity. The CAD/AI system acts as a supplement to human readers and marks potential areas of concern so the radiologist can decide if the area warrants further investigation. It can assist radiologists to identify cancers, which might otherwise be missed. There has been widespread use of CAD/AI systems in breast cancer screening programs particularly in the United States’ Medicare population where it is estimated it is used in 74% of screening

IP1 - PROSTAGRAM	Protocol No: 18HH4595	Sponsor: Imperial College London	V 1.2 01MAY2019
-------------------------	---------------------------------	--	------------------------

mammograms(35). There is extensive evidence that the system can improve the sensitivity of mammography and improve radiology reporting workflow (36). CAD/AI systems are being investigated in other image-based screening modalities particularly CT-colonography with encouraging results(37).

There are similar CAD/AI systems available for prostate MRI and in the early stage of validation (38). The PROSTAGRAM study will embed a CAD/AI application to prospectively evaluate the feasibility of using a CAD/AI system within the workflow of radiological interpretation.

1.3 Recruitment Strategies

Screening tests are targeted at a large population of asymptomatic individuals, the majority of whom are healthy and do not have the target disease. The low prevalence of positive findings from screening necessitate a large sample size to evaluate performance characteristics of screening tests. Potential participants are recruited direct from the community, which requires different strategies to trials recruiting within existing clinical pathways.

The PROSTAGRAM trial will evaluate various recruitment pathways in order to establish the optimum recruitment strategy and identify potential barriers to recruitment. These include postal, sms, poster, websites and direct opportunistic approaches via the general practitioner.

Previous prostate cancer screening trials have used written invitations with subsequent 45% response rate to attend a prostate cancer-screening clinic (39). This is lower than the uptake for breast and cervical screening which have uptake rates consistently above 70%, although these are in the context of a national screening programme with extensive resources, advertising and public acceptance. A low uptake can have significant impact on the external validity of a screening test(40).

In addition, previous large screening trials have had a low screening uptake among certain ethnic groups. African/African-Caribbean men have been particularly under-represented in previous trials despite being at double the risk of mortality from prostate cancer (41). The current screening strategies are based on recommendations from studies of predominately Caucasian men despite the clear evidence that African/African-Caribbean men have a high lifetime risk of prostate cancer mortality. There is a need for further screening research in this population and the PROSTAGRAM study aims to achieve a participant recruitment which is representative across ethnic risk groups particularly African/African-Caribbean men.

1.4 Rationale for study

The UK National Screening Committee has recommended that further research is required into alternative screening tests before a population-based prostate cancer screening programme can be considered for approval(42). We propose that prostate MRI has certain performance characteristics, which make it attractive as a potential screening test. We have previously shown that prostate is a reliable pre-biopsy triage test in secondary care once

IP1 - PROSTAGRAM	Protocol No: 18HH4595	Sponsor: Imperial College London	V 1.2 01MAY2019
-------------------------	---------------------------------	--	------------------------

men have been referred to hospitals for an elevated serum PSA. However, its role as a screening test is unknown and warrants further investigation.

Our long-term objective is to evaluate whether a screening prostate MRI could be an alternative or complementary image-based screening test to PSA.

The current study has not been designed to establish the sensitivity and specificity of MRI as this would require all participants to undergo a prostate biopsy as the reference standard for determining the presence of prostate cancer. It would not be appropriate in a screening study to require all participants to have a biopsy particularly when the diagnostic performance of prostate MRI has been well established in secondary care with prostate biopsy as the reference standard.

Instead, the primary objective will be to establish the prevalence of screen-positive prostate MRI in the general male population aged 50-69 years and collect information on the feasibility of a larger scale study. The results of this study will inform the design of a large diagnostic paired cohort validating study comparing PSA and MRI and other potential imaging or fluidic biomarkers. The subsequent study requires a large sample size and resource commitment due to the low prevalence of prostate cancer in a screened population. In this study, we will obtain point estimates on the prevalence of a suspicious test that triggers a biopsy; such information is currently not available and is required to inform the design and sample size calculations of the larger clinical study. This study will also evaluate the feasibility of a large screening MRI trial. We will optimise recruitment strategies and identify potential barriers to recruitment.

2. OBJECTIVES AND ENDPOINTS

2.1 Primary Objective

To determine the positive test rate of prostate MRI in the general male population aged 50 to 69 years

2.2 Other test performance objectives (MRI and US)

1. To determine the prevalence of positive test rate of prostate ultrasound in the general male population aged 50 to 69 years
2. To determine the distribution of MRI and US scores in a screened population
3. To evaluate a suitable threshold score that defines positivity of MRI or US in a screening population
4. To estimate the overall agreement between PSA, US and MRI in the proportion of men with a positive result. Then to compare the overall agreement in proportion of men diagnosed with clinically significant prostate cancer on biopsy.

IP1 - PROSTAGRAM	Protocol No: 18HH4595	Sponsor: Imperial College London	V 1.2 01MAY2019
-------------------------	---------------------------------	--	------------------------

5. To explore combinations and sequences of prostate MRI, US and PSA that might be an optimal screening strategy to evaluate in a future definitive study
6. To estimate the overall agreement of Imaging findings, PSA and DRE
7. To report the clinical outcomes of men with a positive PSA, US and/or MRI result

2.3 Fluidic Biomarker objectives

1. To determine the positive test rate and the distribution of biomarker panel scores in the general male population aged 50 to 69 years
2. To collect and store serum and urine samples in a biobank to evaluate new serum biomarkers

2.4 Feasibility Objectives

1. To evaluate the feasibility of undertaking a screening cohort study comparing the diagnostic performance of prostate MRI and/or US and/or serum prostate specific antigen (PSA) testing
2. To determine the recruitment rates to the study across different ethnic groups
3. To determine the eligibility rates across each screening test
4. To determine the compliance/retention of participants with study processes
5. To assess the acceptability of study processes and informational content.
6. To estimate the costs of undertaking a subsequent diagnostic paired cohort validating study

2.5 Reporting and CAD/AI Objectives

1. To evaluate the diagnostic performance of a CAD/AI algorithm as a standalone reader
2. To evaluate the effect of CAD/AI as a second reader on diagnostic performance of radiologists
3. To evaluate the effect of CAD/AI on interobserver variability of radiological interpretation of prostate MRI
4. To define a suitable threshold MAI score to detect clinically significant cancer

2.6 Other Objectives

1. To determine the health-related quality of life outcomes

IP1 - PROSTAGRAM	Protocol No: 18HH4595	Sponsor: Imperial College London	V 1.2 01MAY2019
-------------------------	---------------------------------	--	------------------------

2. To assess risk perception and prostate cancer worry and anxiety of prostate cancer during the study
3. To establish the prevalence of post-biopsy adverse events
4. To collect the long-term health outcomes of those men who consent to longitudinal follow-up
5. To build a databank of ultrasound and MRI meta-files matched with histopathology for future research and education

2.7 Primary Endpoint

The proportion of men with a screen-positive MRI defined by a score of 3 or greater.

2.8 Performance objectives (MRI and US)

1. The proportion of men with screen-positive prostate ultrasound defined by a score of 3 or greater
2. The proportion of participants within each MRI score or US score of 1, 2, 3, 4 or 5
3. An evaluation of proportion of participants across each MRI and US score with no cancer, insignificant cancer and significant cancer with each test.
4. A comparison of the proportion of participants with a positive result for each screening test. A comparison of the proportion of men subsequently diagnosed with a clinically significant prostate cancer as defined by pre-specified histological definitions
5. Comparison of different testing combinations in terms of biopsy rates, detection of insignificant cancer and significant cancers
6. The correlation between imaging findings and DRE
7. The proportion of men who go onto definitive local or systemic treatment. In men who undergo radical prostatectomy the proportion who are upgraded at final histology

2.9 Fluidic Biomarker objectives

1. The proportion of participants within a positive Episwitch biomarker panel and distribution of score
2. To establish a biobank of fluidic samples matched with histopathology for future research

2.10 Feasibility

1. Feasibility will be measured based on a point-estimate of recruitment rates across different recruitment strategies. Recruitment rates will be defined as the number of individuals who:
 - i. Contact the study team with an expression of interest in participation
 - ii. Attend the screening clinic
 - iii. Offer informed consent and are enrolled into the study

IP1 - PROSTAGRAM	Protocol No: 18HH4595	Sponsor: Imperial College London	V 1.2 01MAY2019
-------------------------	---------------------------------	--	------------------------

These results will enable a prediction of number of General Practitioner (GP) practices and length of time needed to recruit the required number of patients for a future trial.

2. The proportion of men from different ethnic groups accepting the initial invitation to participate and subsequently participating within the study
3. Eligibility will be assessed against pre-defined eligibility criteria. The reasons for ineligibility will be recorded and compared across each screening test
4. The retention/compliance rate will be defined as the number of participants completing screening tests and any follow-up biopsy recommendation. The reasons for withdrawal will be documented with an optional survey offered to individuals.
5. The individual costs for recruitment and screening will be recorded in a resource utilisation log. These will be scaled up to provide an estimate of the cost for the subsequent study

2.11 **MRI Reporting and CAD/AI Objectives**

1. Sensitivity analysis of the CAD/AI system with histology and/or radiologist consensus as the reference standard
2. Comparison of radiologist diagnostic performance for detection of clinically significant cancer with and without the CAD/AI
3. The Intraobserver agreement with and without the use of CAD/AI as second reader
4. Receiver operating characteristic (ROC) to compare the diagnostic performance of CAD/AI at different MAI scores

2.12 **Other**

1. Changes in HRQOL measured by SF-12 and at baseline and follow-up
2. Changes in worry and anxiety scores measures by CWS and STAI.
3. Rates of biopsy related adverse events (infectious complications, urinary retention, and haematuria requiring admission)
4. Linkage to national database
5. An open access secure and quality controlled databank of ultrasound and MRI meta-files matched with histopathology for future research and education

2.13 **Definition of clinically significant cancer**

Clinically significant cancer will be defined across a range of histological thresholds including

- i. Any length of Gleason $\geq 3+4$
- ii. Any length of Gleason $\geq 4+3$
- iii. UCL/[name] definition 1 (Gleason $\geq 4+3$ and/or Maximum cancer core length $\geq 6\text{mm}$).
- iv. UCL/[name] definition 2: Gleason $\geq 3+4$ and/or Maximum cancer core length $\geq 4\text{mm}$
- v. Gleason $\geq 3+4$ and/or Maximum cancer core length (MCCL) $\geq 6\text{mm}$

IP1 - PROSTAGRAM	Protocol No: 18HH4595	Sponsor: Imperial College London	V 1.2 01MAY2019
------------------	--------------------------	-------------------------------------	-----------------

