	To establish a biobank of fluidic samples matched with histopathology for future research	Total number of men providing specimens to the tissue biomarker	Visit 1: Biobank entry log
FEASIBILITY	To evaluate the feasibility of a screening cohort study investigating the diagnostic performance of prostate MRI vs. PSA	Descriptive statistics of recruitment rates	Visits 1 & 2: Recruitment log/form
	To determine the recruitment rates across different ethnic groups	Proportion of men from different ethnic groups recruited to study	Visit 1 & 2: Recruitment log/form
	To determine the eligibility rate across each screening test	The number of men with reasons for ineligibility	Visit 1: Recruitment log
	To determine the compliance/retention of participants with study processes	Number of men completing tests & follow up recommendations	Visits 1-3: Recruitment log/form
	The acceptability of study processes and informational content	Thematic analysis of interviews and free texts	Acceptability Questionnaires
	The costs of undertaking a diagnostic paired cohort validating study	Scaled up costs of recruitment & screening	Resource utilisation log

IP1 - PROSTAGRAM	Protocol No: 18HH4595	Sponsor: Imperial College London	V 1.2 01MAY2019
-------------------------	---------------------------------	--	------------------------

[figure not shown]
OBJECTIVES		ENDPOINT	TIME POINT & TOOL
CAD/AI	To evaluate diagnostic performance of a CAD/AI algorithm as a standalone reader to detect clinically significant prostate cancer on MRI	Sensitivity analysis of the CAD/AI system with biopsy or consensus as the reference standard	Visit 1 & 2: MRI, CAD and biopsy reporting form
	To evaluate the effect of CAD/AI as a second reader on diagnostic performance of the radiologist	Comparison of diagnostic performance of radiologists with and without CAD	Visit 1 & 2: MRI, CAD and biopsy reporting form
	To evaluate the effect of CAD/AI on interobserver variability of radiological interpretation of prostate MRI	Interobserver agreement quantified	Visit 1 & 2: MRI, CAD and biopsy reporting form
	To define a suitable threshold MAI score to detect clinically significant cancer	ROC comparing diagnostic performance of CAD/AI at different MAI scores	Visit 1 & 2: CAD output and biopsy reporting time
OTHER	To determine the health-related quality of life outcomes	Change to SF-12 at baseline and follow-up	Visit 1, 2 & 3: Questionnaires at baseline and follow-up

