5 PROCEDURES AND MEASUREMENTS

5.1 Identification and recruitment of patients

5.1.1 GP Practice Recruitment

GP practices will be recruited from each individual study region. The initial recruitment will be from practices within the North West London study region in collaboration with the NIHR Clinical Research Network North West London (CRN NWL). The CRN NWL will approach GP practices, and the study team GP practices will continue to be added to ensure the sample size is achieved. Anonymised data will be extracted from all participating practice computer systems related to the demographics of the practice population. This data will be used to describe the general practice population and ensure that recruitment is representative across each practice.

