5.1.2 Participant Recruitment

Figure 2 summarises the recruitment flow chart. A number of approaches will be used to inform potential participants about the trial and undertake recruitment:

Postal invitation

For practices using the postal invitation approach, potential participants will be identified from the GP practice registers. The practice database will be searched using pre-defined eligibility criteria including PSA results, history of prostate cancer and the presence of other co-morbidities. This data will be used to assess the patient's suitability to participate, including whether the patient's co-morbidity and/or frailty means that an individual's life expectancy would limit their benefit from screening or other reasons why it may be inappropriate for the patient to receive an invitation.

Participants deemed eligible will be sent an SMS or invitation letter with an enclosed leaflet depending on the GP practice policy. Research shows that the majority of participants make their informed decision on whether to participate in research based on shortened first level information(45). The participation postal recruitment procedures are detailed in a Standard Operating Procedure (SOP Postal Recruitment). Non-responders may be sent up to one reminder and/or telephone call or SMS message via the general practitioner depending on the services available in each surgery. The patient list will be used to provide basic, anonymised information regarding non-responders for comparison with the recruited cohort. This will enable some assessment of how representative the recruited cohort is for each GP Practice.

Opportunistic recruitment:

In practices using opportunistic recruitment, eligible individuals presenting to their GP for a routine consultation will be informed about the study and invited to participate. Potential participants may also be opportunistically approached by their GP during a home visit. The GP will check eligibility criteria and discuss the basic structure of the study. If the individual is interested, they will be offered an invitation letter directly along with the documents listed

IP1 - PROSTAGRAM	Protocol No: 18HH4595	Sponsor: Imperial College London	V 1.2 01MAY2019
-------------------------	---------------------------------	--	------------------------

above and asked to contact the study team. Posters and flyers may also be put on display at participating GP surgeries

Supplementary Recruitment strategies

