6. INTERVENTION (IF APPLICABLE)

6.1 Baseline Assessments

After obtaining informed consent and registering the patient in the study the following clinical and baseline assessments will be undertaken:

- A clinical history and review of concomitant medications.
- Specific history related to family history of prostate cancer and urinary symptoms.
- Ethnicity will be recorded.
- Physical examination including digital rectal examination (DRE)
- IPSS, SF-12, CWS and STAI questionnaire

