## 10. Variables of Analysis

### 10.1. Baseline Demographic Variables

After obtaining informed consent and registering the patient in the study, the following clinical and baseline assessments will be undertaken:

- Demographics such as: age, Index of Multiple Deprivation (IMD) quintile, BMI, ethnicity, qualification level, marital status, employment status, frequency of GP visits, smoking status and history, how the patient heard about the prostate check and, Digital rectal examination (DRE) results.
- Specific family, medical and prostate history.
- CCI and IPSS questionnaires (see Appendix 1).

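### The ethnic-group uptake end point is specified in two ways without a denominator, and no specified data source gives the ethnicity of men lost between first contact and consent

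*Protocol*

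**What the plan says.** Protocol 2.4 lists recruitment rates by ethnic group as a feasibility objective. The matching end point in Protocol 2.10 item 2 is "The proportion of men from different ethnic groups accepting the initial invitation to participate and subsequently participating within the study". SAP 4.2.3 item 2 and the Protocol's Trial Summary carry the same two-stage wording.

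Table 2.14 of the Protocol pairs the objective "To determine the recruitment rates across different ethnic groups" with the end point "Proportion of men from different ethnic groups recruited to study". The source given is the recruitment log or form at Visits 1 and 2.

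On data capture, Protocol 6.1 opens "After obtaining informed consent and registering the patient in the study the following clinical and baseline assessments will be undertaken" and includes in the list that follows: "Ethnicity will be recorded". SAP 10.1 also puts ethnicity under "After obtaining informed consent and registering the patient in the study, the following clinical and baseline assessments will be undertaken". The visit schedule in Protocol 5.4 places demographics at the screening visit; the telephone column covers only eligibility and explanation of procedures.

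Two practice-level sources precede consent. Protocol 5.1.1 says "Anonymised data will be extracted from all participating practice computer systems related to the demographics of the practice population". Protocol 5.1.2 says "The patient list will be used to provide basic, anonymised information regarding non-responders for comparison with the recruited cohort". Neither lists its variables. Section 5.1.2 also sets up a screening and enrolment log, for which the stated content is the reasons for declining and for ineligibility.

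**The concern.** The two-stage end point asks, within each ethnic group, how many men accepted and how many of those went on to take part. The recruited-only version drops the first stage. If ethnicity is taken only from men who have consented, the study will know the make-up of its cohort but not where each group was lost.

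That matters for the study's own aims. Protocol 1.3 notes that African/African-Caribbean men were under-represented in earlier screening trials and says the study seeks recruitment that is representative across ethnic risk groups. Protocol 1.4 says it will identify barriers to recruitment for a larger trial. A small share of one group among recruits could mean that the group was not reached, declined, or was lost between contact and consent. These call for different remedies, and composition alone does not separate them.

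**Working it through.** The plan gives no figure for this end point, so there is none to reproduce. The check is a comparison of sections, followed by an illustration of what composition can and cannot show.

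**Definition.**

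| Place | Stages named | Denominator |
|---|---|---|
| Protocol 2.10 item 2 | accepting, then participating | not stated |
| SAP 4.2.3 item 2 | accepting, then participating | not stated |
| Protocol 2.14, end point column | recruited | not stated |
| Protocol 2.14, objective column | recruitment rates | not stated |

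Protocol 2.10 item 1 names three recruitment stages (contact, attendance, consent) but defines them as numbers of individuals, so it does not supply the missing denominator either.

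**Where ethnicity could come from.**

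| Group of men | Source named | Is ethnicity stated? |
|---|---|---|
| Practice population (GP routes) | practice extract, Protocol 5.1.1 | not stated either way |
| Postal/SMS non-responders | patient list, Protocol 5.1.2 | not stated either way |
| Made contact, then declined or ineligible | screening log, Protocol 5.1.2 | not named; reasons only |
| Reached by poster, website, social media or word of mouth and never made contact | none | no count of men reached |
| Consented | baseline assessment, Protocol 6.1 and SAP 10.1 | yes |

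If the practice and non-responder data carry ethnicity, men invited minus non-responders would give acceptance by ethnic group for the letter and SMS routes. They would still not give the ethnicity of self-referred men who make contact and then drop out.

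**Why composition is not uptake.** From the documents: 4,800 letters (Protocol 9.2) and 406 enrolled (Protocol 5.5). Assumed, not in the documents: all 406 come from the letters, and one ethnic group makes up 10% of those enrolled, which is 0.10 × 406 = 40.6 men, leaving 365.4 others. Let s be that group's share of the men invited.

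Uptake in the group = 40.6 / (4,800 × s). Uptake in other men = 365.4 / (4,800 × (1 − s)).

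| s | Uptake in the group | Uptake in other men |
|---|---|---|
| 5% | 40.6/240 = 16.9% | 365.4/4,560 = 8.0% |
| 10% | 40.6/480 = 8.5% | 365.4/4,320 = 8.5% |
| 20% | 40.6/960 = 4.2% | 365.4/3,840 = 9.5% |

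The same composition fits a four-fold range of uptake. The number invited, by ethnic group, is what distinguishes these cases.

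**The case against.** The strongest reply is that the documents are silent here rather than wrong. Table 2.14 names the recruitment log, not the baseline form, as its source. That log covers men being considered for the trial, and its full field list is not given. Recruitment and CRF detail is left to an SOP and a CRF manual. Protocol 6.1 says that ethnicity is recorded at baseline; it does not say that it is recorded at no other time. A demographic extract could well include ethnicity. Table 2.14 is condensed, and its own objective speaks of rates. The 2.10 wording is itself open to two readings: the ethnic mix of acceptors, or a rate within each group. The SAP's introduction confines version 1 to the primary outcome paper and leaves the feasibility and recruitment paper to amendments. Poster, media and word-of-mouth routes have no countable invited population whatever is recorded.

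Much of this stands. A reader might infer that uptake by ethnic group is impossible to score, or that 2.14 formally redefines the end point as cohort composition. The documents support neither: the practice data and the log may carry ethnicity, and the 2.14 objective points towards rates. Nor do the documents say how many responders will be lost before consent, or from which groups, so no count of affected men can be given.

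Three points remain. The acceptance stage is missing from the 2.14 end point. No denominator is stated. No section names ethnicity as a field for men lost between contact and consent. Deferring the analysis does not cure the last, because an answer not requested at first contact cannot be obtained later from men who never enrol.

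**Conclusion.** The point holds as a gap in specification and data capture. The definitions in 2.10 and the SAP on one side and 2.14 on the other need reconciling, and each stage needs a denominator. Followed as written, the plan leaves men who make contact but do not consent without a recorded ethnicity. An invitation-stage rate by ethnic group may be available for the GP letter and SMS routes, if the practice and non-responder data include ethnicity; this should be confirmed rather than assumed.

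The illustrated range of 4.2% to 16.9% rests on an assumed 10% share of recruits, assumed invited shares of 5% to 20%, and recruitment by post alone. It shows that composition does not determine uptake; it does not predict this study's results. The issue affects one secondary feasibility end point and leaves the primary end point, the proportion of men with a positive MRI, untouched. It is worth acting on because the end point serves a stated objective and the remedy is cheap while recruitment is open.

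**What to change.** 1. Ask for self-reported ethnicity, as an optional question, at first contact (telephone screening or the online form) and hold it in the screening log.
2. Make sure that ethnicity is included in the practice extract (Protocol 5.1.1) and in the non-responder data (5.1.2), and say so in the Protocol.
3. Use one definition in Protocol 2.10, table 2.14 and the SAP amendment for the feasibility paper, with a numerator and denominator for each stage. Copying the 2.10 wording into 2.14 would not be enough, since it has no denominator.
4. Within each ethnic group, and for all routes, report the proportions moving from contact to attendance and from attendance to consent.
5. Limit the invitation-acceptance rate to routes with a known number invited.
6. Report cohort composition by ethnic group as a separate line, with the number of men who did not state their ethnicity at each stage.

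The cost is one optional log field, a check on two data extracts already planned, and a minor protocol amendment. Some men will decline to answer, so the early-stage proportions will carry some missing data.
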